13.5.1 NPRS

The primary efficacy endpoint is the absolute change from baseline mean NPRS score to the end of treatment NPRS score after LAT8881, compared with the change from baseline after placebo treatment.

Daily NPRS scores for all enrolled subjects will be listed only. Mean and standard deviation of scores during the baseline period and weeks 1, 2, 3 and 4, and the absolute and percentage change from baseline in each period, will be listed for each subject and summarised for LAT8881 and placebo treatments overall and within treatment sequence for all randomised subjects and for the PP population. The maximum change in mean NPRS from baseline to weeks 1, 2, 3 and 4, determined for each subject after LAT8881and placebo, will be listed and summarised.

Mixed effects regression models will be used to compare the absolute and percentage changes from baseline to the end of each treatment for the mean NPRS scores. The models will have fixed effects for period and treatment. Baseline mean pain score within each period by treatment combination will be included as a covariate. A random effect for subject will be included to capture the repeated measures nature of the design.

The models for the primary endpoint will be expanded to compare the absolute and percentage changes from baseline for the mean NPRS scores after 1, 2 and 3 weeks of dosing with IMP in each treatment period. The model will also include a fixed effect for week (1, 2, 3 and 4), the interaction between treatment and week to assess whether the change from baseline for each treatment is different.

The mean score at each visit, change from baseline, difference between treatments in the change from baseline and corresponding 95% confidence intervals will be presented. Comparisons will be declared statistically significant if p<0.05.

In PK subjects, NPRS scores at specified times up to 6 hours on Days 1, 28, 50 and 77 will be listed and summarised. Change from pre-dose values will also be listed and summarised. Changes over time will be analysed using the same modelling approach as for the primary endpoint.

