3.2 Secondary Objectives

1. *To investigate the effect of oral LAT8881 in NP compared with placebo at different timepoints (up to 6 hours) following a single dose and after 4 weeks treatment, as measured by the NPRS (PK subjects only)*
2. *To investigate the effect of oral LAT8881 on mean pain scores in NP compared with placebo after 1, 2 and 3 weeks of dosing, as measured by the NPRS*
3. *To determine the proportion of responders to oral LAT8881 in NP compared with placebo*
4. *To investigate the maximum effect of oral LAT8881 in NP compared with placebo, as determined by the maximum change from mean NPRS baseline after 1, 2, 3 or 4 weeks treatment*
5. *To evaluate the effect of oral LAT8881, compared with placebo, on functioning in subjects with NP when measured by the 7-item short form Brief Pain Inventory (BPI) Interference Scale*
6. *To evaluate the effect of oral LAT8881, compared with placebo, on pain symptoms in subjects with NP when measured by the short-form McGill Pain Questionnaire 2 (SF-MPQ-2)*
7. *To evaluate the effect of oral LAT8881, compared with placebo, on symptoms in subjects with NP, when measured by the Neuropathic Pain Symptom Inventory (NPSI)*
8. *To evaluate the effect of oral LAT8881, compared with placebo, on emotional functioning when measured by the Beck Depression Inventory-II (BDI-II)*

9. To evaluate the effect of oral LAT8881, compared with placebo, on overall health and quality of life in subjects with NP, when measured by the Patient Global Impression of Change (PGIC) scale
10. To determine the change from baseline in rescue medication use during oral LAT8881 administration, compared with placebo
11. To evaluate the safety and tolerability of oral LAT8881 in NP after a single dose and after four weeks treatment
12. To investigate the pharmacokinetics of twice daily oral LAT8881 in 15 subjects with NP after a single dose and after 4 weeks treatment with oral LAT8881

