11.6.1.2 Mixed Effect Regression Model

A mixed effects regression model using a covariance pattern will be fitted to the absolute change from baseline mean NPRS scores at weeks 1, 2, 3 and 4 within each treatment period for the PP population. This analysis will provide the results for the primary efficacy endpoint (change from baseline to week 4) and for the secondary endpoint (change from baseline to weeks 1, 2 and 3).

The model will have fixed effects for period, week, treatment and the interaction between week and treatment. Baseline mean pain score within each period by treatment combination will be included as a covariate. A random effect for subject will be included to capture the repeated measures nature of the design.

Least squares means and corresponding 95% confidence intervals (CI) will be presented for the mean change from baseline for LAT8881, Placebo and difference between LAT8881 vs. placebo at each visit.

P-values for testing the null hypothesis that the difference in least squares means between LAT8881 and placebo at each visit is 0 will be declared statistically significant if the p-value < 0.05.

The covariance pattern will take into account the covariance between observations in different treatment periods and the covariance between observations within the same period (i.e between weeks).

```
proc mixed data=;  
class <subject> <study period> <treatment> <week>; model  
<change> = <baseline> <study period> <week> <treatment>;  
random <subject> <subject>*<period>; lsmeans <treatment>  
<week> / pdiff;  
run;
```

The model will also be fitted to the absolute change from baseline in mean NPRS ratings for the FAS population. Extent of sensitivity analyses of missing data patterns to be undertaken will be decided during the blinded review meeting. In DDP: Tables 14.2.2.1 to 14.2.2.2

11.6.1.2.1 *NPRS at timepoints*

A mixed effects regression model using a covariance pattern will be fitted to the absolute change from pre-dose NPRS scores at timepoints 0.5, 1, 2, 4 and 6 hours post-dose at baseline and week 4 visits within each study period for the per-protocol subjects with NPRS collected at timepoints in baseline and week 4 visits.

The model will have fixed effects for period, week, timepoint and the interaction between week and timepoint. Pre-dose pain score within each week will be included as a covariate. A random effect for subject will be included to capture the repeated measures nature of the design.

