Least squares means and corresponding 95% confidence intervals (CI) will be presented for the mean change from pre-dose for each timepoint at each visit. P-values for testing the null hypothesis that the difference in least squares means across timepoints at each visit will be declared statistically significant if the p-value < 0.05.

The covariance pattern will take into account the covariance between observations in different treatment periods and the covariance between observations within the same period (i.e between weeks).

```
proc mixed data=;  
class <subject> <timepoint> <week>; model  
<change> = <baseline> <week> <timepoint>; random  
<subject> <subject>*<week>; lsmeans <timepoint>  
<week> / pdiff; run;
```

In DDP: Tables 14.2.2.3

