11.7.3.4 Electrocardiogram Assessments

Number and percentage of subjects with overall findings (Normal, Abnormal Not CS and Abnormal CS) will be summarized by treatment overall and within each study period and visit. Percentages will be based on safety population.

In DDP: Table 14.3.6.1

ECG findings will be listed by treatment sequence, subject ID, treatment period and visit.

In DDP: Listing 16.2.9.3

12 Changes to Planned Analyses

- Mixed Effect Regression analyses for change from baseline in NPRS mean scores is combined for weeks 1-4 within the same model, instead of week 4 and weeks 1-3 separately as defined in study protocol.
- McNemar's test is included to compare proportion of subjects achieving $\geq 30\%$ and $\geq 50\%$ reduction in mean NPRS scores across study periods.
- Analysis of covariance is included to see the effect of treatment and placebo in maximum reduction from baseline adjusting for baseline NPRS mean scores and time taken to reach maximum reduction.
- Mixed Effect Regression analyses for change from baseline in NPRS mean scores including clinical diagnosis (PHN, DPN) and baseline [REDACTED] as additional covariates is

considered as secondary analyses instead of exploratory analyses since subgroups PHN and DPN were considered clinically relevant.

- PK Analyses is not included in this Statistical Analysis Plan, and will be done separately. PK Population is replaced with Per-Protocol population for subjects with NPRS assessments taken at timepoints in baseline and Week 4 visits.

13 Index of Tables, Listings and Graphs

Refer LAT-NP-001_Data Display Plan (Ver: 2.00) for the list of Tables, Listings and Graphs.

14 References

1. ICH. ICH Harmonized Tripartite Guideline: Statistical Principles for Clinical Trials E9. 1998.
2. ICH. ICH Harmonized Tripartite Guideline: Structure and Content of Clinical Study Reports E3. 1995.

15 Appendices

15.1 painDETECT questionnaire

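### The model for NPRS in the 6 hours after dosing has no treatment term, so it cannot compare LAT8881 with placebo as secondary objective 1 requires

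*SAP*

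**What the plan says.** **Objective.** SAP 3.2, item 1, reads: "To investigate the effect of oral LAT8881 in NP compared with placebo at different timepoints (up to 6 hours) following a single dose". It continues to the same question after 4 weeks and is limited to PK subjects.

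**Protocol analysis.** Protocol 13.5.1 says of these readings: "Changes over time will be analysed using the same modelling approach as for the primary endpoint". For the primary endpoint the same section states: "The models will have fixed effects for period and treatment".

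**SAP model.** SAP 11.6.1.2.1 (NPRS at timepoints) says:
- Fixed effects: "The model will have fixed effects for period, week, timepoint and the interaction between week and timepoint", with the pre-dose score as covariate.
- Code, fixed part: `"<change> = <baseline> <week> <timepoint>"`.
- Code, random part and LS means: `"<subject> <subject>*<week>; lsmeans <timepoint>"`, followed by week.
- Null hypothesis: "the difference in least squares means across timepoints at each visit".

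**Declared changes.** On these data SAP section 12 lists only this: "PK Population is replaced with Per-Protocol population for subjects with NPRS assessments taken at timepoints in baseline and Week 4 visits".

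**The concern.** The objective is a comparison with placebo, but treatment appears nowhere in the inferential analysis meant to serve it. The weekly NPRS model in SAP 11.6.1.2, directly above, names treatment in its text, code, LS means and hypothesis. The timepoint model names it in none of these, so a single coding slip is an unlikely explanation.

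A significant result from the model as written would show that pain changed over the clinic day with drug and placebo data pooled. Placebo response or ordinary drift could produce that. Changes from pre-dose (SAP 7.2, items 1 and 2) would still be summarised, but there would be no estimate, interval or test against placebo. If the comparison is added after unblinding, it becomes post hoc.

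**Working it through.** **1. The plan's own figures.** SAP 4.2 gives SD 2, correlation 0.5, difference 1 unit, 90% power and 20% dropout; SAP section 8 gives two-sided 5%. The SD of the within-subject difference is √(2 × 2² × (1 − 0.5)) = 2.0. A paired t test with n = 44 has power 0.900, and 44 / 0.8 = 55. The stated 44 and 55 reproduce. They do not bear on the omission, but the same SD and correlation are used in step 4.

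**2. Can any term stand in for treatment?** Take 15 crossover subjects, 2 periods, 2 visit types and 5 timepoints, which is 15 × 2 × 2 × 5 = 300 readings. With 12 completers it is 240, plus any period 1 readings from subjects who drop out.

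| Model | Fixed-effect columns | Rank | Rank with treatment appended |
|---|---|---|---|
| SAP text | 1 + 1 + 1 + 1 + 4 + 4 = 12 | 12 | 13 |
| SAP code | 1 + 1 + 1 + 4 = 7 | 7 | 8 |
| Text plus treatment and its interactions with week and timepoint | 12 + 1 + 1 + 4 + 4 = 22 | 22 | 22 |

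The columns for the text model are intercept, pre-dose score, period, week, timepoint and week by timepoint; the code drops period and the interaction. In both, appending treatment raises the rank, so LAT8881 minus placebo is not estimable from the fitted effects. Period cannot replace treatment, because each period contains both. In the 22-column model the contrast is estimable: adding a true 1-point effect to simulated data moved the treatment coefficient from −0.504 to −1.504.

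**3. What the pooled means hide.** For subjects with both periods, take the change at 2 h relative to 0.5 h:
- LAT8881 −1.0, placebo 0: pooled (−1.0 + 0)/2 = −0.50, the same as −0.50 on both.
- LAT8881 −1.0, placebo −0.5: pooled (−1.0 − 0.5)/2 = −0.75, the same as −0.75 on both.

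**4. Precision once treatment is added.** The documents give no SD for post-dose change, so the primary endpoint's values are assumed. The half-width is t(n − 2) × 2√(2(1 − ρ)) / √n. For n = 15 and ρ = 0.5 this is 2.160 × 2.0 / √15 = 1.12.

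| n | ρ | Half-width | Power for 1 unit |
|---|---|---|---|
| 15 | 0.3 / 0.5 / 0.7 | 1.32 / 1.12 / 0.86 | 33 / 43 / 64% |
| 12 | 0.3 / 0.5 / 0.7 | 1.52 / 1.29 / 1.00 | 26 / 35 / 52% |

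**5. Is adding treatment alone enough?** The code's random terms are subject and subject by week. A subject's drug and placebo visits of the same visit type therefore form one cluster of 10 readings. Assume variances of subject 1, subject by period 0.5, visit 0.5 and residual 1 (not from the documents), with n = 15.
- True SE of the difference at one visit type, averaged over timepoints: √(2 × (0.5 + 0.5 + 1/5) / 15) = 0.40.
- Residual variance the model would see: (5 × 1.0 + 9 × 1) / 9 = 1.556. Model SE: √(2 × 1.556 / (5 × 15)) = 0.20.
- Ratio 1.96. Against a t critical value on 13 df (2.160), type I error is P(|Z| > 2.160/1.96), about 27%. Varying the visit variance from 0.25 to 1.0 gives about 24–32%.
- At a single timepoint the true SE is √(2 × 2 / 15) = 0.52 and the model SE √(2 × 1.556 / 15) = 0.46, giving about 5.7%.

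REML simulation under the null, with the same variances:

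| Random terms | Runs | Type I error, averaged | Type I error, 2 h only |
|---|---|---|---|
| SAP code | 357 | 26.9% | 6.7% |
| Per-visit fit: subject, subject by period | 400 | 4.3% | 2.8% |
| Joint fit: subject, subject by period, visit | 274 | 3.6% | 2.2% |

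**The case against.** The absence of treatment is not in dispute. The case on the other side concerns what is built on it.

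- *The protocol wording refers to changes over time, and a test across timepoints is a literal reading of that.* This weakens the charge that a protocol term was dropped, but the conflict with the objective remains.
- *The section 11 default is summaries by treatment, and post-dose PK work is outside the SAP.* The default covers summaries, not model terms, and SAP 11.6.1.1.1 names only study period and total for this table. The Data Display Plan was not available, so the table layout is a point to clarify. Post-dose NPRS is a secondary efficacy endpoint that the SAP keeps and models.
- *The 27% error rate belongs to an analysis nobody proposed, under assumed variances, for a timepoint-averaged contrast.* This stands. At a single timepoint the inflation is small; an exact 95% CI for the simulated 6.7% is 4.4–9.8%, which includes 5%. The figure is a warning about an incomplete repair, and the main finding does not depend on it.
- *The SAP says the covariance pattern will allow for covariance between and within treatment periods.* The intent is therefore stated, but the code has no period term and does not carry it out. The weekly model's code also omits an interaction its text promises, so code that falls short of its text is not unique to this section.
- *It is one secondary objective in about 15 subjects, without multiplicity control.* True, and this limits the severity.

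**Conclusion.** The concern holds. Followed as written, SAP 11.6.1.2.1 yields no LAT8881–placebo difference, confidence interval or p-value for secondary objective 1, at either visit type. This follows from the model specification and needs no assumption about the data. The omission is not declared in section 12. The code also lacks the period and week-by-timepoint terms that its own text lists.

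The precision figures assume that the primary endpoint's SD carries over. That SD describes a multi-day mean rather than a single reading, and only the correlation was varied. The error rates rest on assumed variance components with exchangeable readings within a visit; serial correlation was not examined.

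This should be fixed before unblinding. It affects one secondary objective and leaves the primary analysis untouched.

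**What to change.** 1. **Model.** The simplest repair is to fit each visit type (first dose, week 4) separately: change from pre-dose on pre-dose score, period, timepoint, treatment and treatment by timepoint, with random subject and subject by period. In a per-visit fit, subject by period identifies the clinic visit, so its five readings are clustered together.
2. **Alternative.** If one joint model is kept, restore period and week by timepoint in the code. Add treatment with its week and timepoint interactions, and use random subject, subject by period, and visit within subject by period, or an equivalent within-visit covariance.
3. **Output.** Report LAT8881 minus placebo with 95% CI at each timepoint for each visit type, and restate the null hypothesis to match.
4. **Table.** State in SAP 11.6.1.1.1 that Table 14.2.1.3 is shown by treatment, overall and within period.
5. **If the omission was deliberate,** declare it in section 12.

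The cost is SAP wording and code, plus table shells if the Data Display Plan follows the current text. Treatment is already a core variable in every analysis dataset (SAP 10.2), so no new data are needed. The result should be presented mainly as an estimate, given its limited precision.

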10.3 Visits

Analysis visits will be defined as follows within each study period:

Visit as per Protocol	Study Period	Analysis Visit
Visit 1 (Days -28 to -1)	Pre-Treatment	Screening

Day 1, Visit 2	Period 1	Visit 2/Visit 5
Day 14, Visit 3	Period 1	Visit 3/Visit 6
Day 28, Visit 4	Period 1	Visit 4/Visit 7
Day 50, Visit 5	Period 2	Visit 2/Visit 5
Day 63, Visit 6	Period 2	Visit 3/Visit 6
Day 77, Visit 7	Period 2	Visit 4/Visit 7
Day 91, Visit 8 or Early Termination	-	EOS / Early Termination

For NPRS scores, post-baseline summaries will be based on weeks within study:

- Week 1 (Days 1-7 and 50-56)
- Week 2 (Days 8-14 and 57-62)
- Week 3 (Days 15-21 and 63-69)
- Week 4 (Days 22-28 and 70-76)

Timepoints will be included for NPRS data as ‘Pre-dose’ and ‘X hours post-dose’ for subjects with measurements taken at timepoints. NPRS will be derived using diary scores as detailed in Section 10.15.

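### The SAS code for the 0.5-6 hour NPRS model omits study period and week-by-timepoint and clusters on subject-by-week, so it contradicts its own text and makes the planned timepoint contrasts too imprecise

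*SAP*

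**What the plan says.** The timepoint model in SAP 11.6.1.2.1 is fitted to changes from the pre-dose score at "timepoints 0.5, 1, 2, 4 and 6 hours post-dose at baseline and week 4 visits within each study period". The text then states: "The model will have fixed effects for period, week, timepoint and the interaction between week and timepoint". It adds a pre-dose covariate and a random subject effect, and says of the covariance: "The covariance pattern will take into account the covariance between observations in different treatment periods", and likewise of ratings within a period. The declared test compares timepoints at each visit at the 5% level.

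The code beneath it reads differently:

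- CLASS: "class <subject> <timepoint> <week>; model"
- MODEL: "<change> = <baseline> <week> <timepoint>; random"
- RANDOM and LSMEANS: "<subject> <subject>*<week>; lsmeans <timepoint>"

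Study period appears nowhere, and the interaction is missing. The main NPRS model in SAP 11.6.1.2 does carry period, with "random <subject> <subject>*<period>; lsmeans <treatment>". Protocol 13.5.1 asks that the PK-subject ratings be analysed with the approach used for the primary endpoint. SAP section 12, which lists departures from the protocol, records no decision to drop period.

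**The concern.** Each PK subject attends four clinic days (Days 1, 28, 50 and 77) and gives five post-dose ratings on each, all measured against that day's single pre-dose score. Ratings from one day share whatever was particular to that day, so the natural cluster is the clinic day: subject by period by week.

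Week has only two levels in this model, because SAP 10.3 pairs Visit 2 with Visit 5 and Visit 4 with Visit 7. A subject-by-week effect therefore ties Day 1 to Day 50 and Day 28 to Day 77. By the crossover, one day of each pair is on LAT8881 and the other on placebo. Differences between the paired days are treated as independent noise on each rating.

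At stake is the precision of a secondary analysis in 15 subjects. Without the interaction, the code also cannot give the visit-specific timepoint means that the text promises; its timepoint means are averaged over the two visits.

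**Working it through.** **Plan's own figure.** The documents give no variance, standard error or power for this model, so there is nothing to reproduce. The trial-level figure does reproduce (SD of the within-subject difference √(2·2²·(1−0.5)) = 2; noncentral t power 0.9000 at n = 44) but has no bearing here.

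**Inputs.** From the documents: 15 subjects, 2 periods, 2 visits per period, 5 timepoints. Assumed: residual variance e, and clinic-day variance d left after the pre-dose covariate, with d/e from 0.5 to 2 and no separate period variance.

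**Step 1, the coded residual.** A subject-by-week cluster holds 10 ratings from two days. Removing its mean leaves 9 degrees of freedom: 8 within days, each with expectation e, and 1 between days, with expectation e + 5d. The residual mean square therefore has expectation, to a close approximation, (8e + e + 5d)/9 = e + 5d/9.

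**Step 2, contrasts between timepoints.** All timepoints occur on every day, so d cancels and the true variance depends on e alone. Coded SE / true SE = √(1 + 5d/(9e)). The actual error rate of a nominal 5% test is 2Φ(−1.96 × ratio).

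| d/e | SE ratio | Actual error rate |
|---|---|---|
| 0.5 | √1.278 = 1.13 | 2.7% |
| 1 | √1.556 = 1.25 | 1.5% |
| 2 | √2.111 = 1.45 | 0.4% |

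The intervals are as wide as a correct analysis would give with about 15/1.278 = 11.7, 15/1.556 = 9.6 or 15/2.111 = 7.1 subjects.

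**Step 3, if treatment were added and the clustering kept.** At one timepoint, true variance is proportional to d + e and coded variance to e + 5d/9. True SE / coded SE = √((1 + d/e)/(1 + 5d/(9e))) = 1.08, 1.13 and 1.19 at d/e = 0.5, 1 and 2. The error rate 2Φ(−1.96/ratio) is then 7.0%, 8.4% and 10.0%.

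For an average over the five timepoints, true variance is (d + e/5)/15 and coded variance is (e + 5d/9)·2/150. The ratio is 1.66, 1.96 and 2.28, giving error rates of about 24%, 32% and 39%.

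**Step 4, simulation.** REML fits to null data, 400 runs per setting, with assumed SDs: subject 0.8, subject-by-week 0.3, residual 0.8 (variance 0.64). The contrast is 6 h against 0.5 h under the SAP code. With period variance present, d in step 2 becomes d plus the period variance.

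| Day SD, period SD | Formula ratio | Simulated ratio | Null rejection |
|---|---|---|---|
| 0, 0 | 1.00 | 0.97 | 6.5% |
| 0.5, 0.5 | √(1 + 0.278/0.64) = 1.20 | 1.16 | 2.0% |
| 1, 0.5 | √(1 + 0.694/0.64) = 1.44 | 1.47 | 1.3% |
| 1, 1 | √(1 + 1.111/0.64) = 1.65 | 1.73 | 0.0% |

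Under the same code the week contrast was about right (ratio 0.96 to 1.02) and the 6 h mean nearly so (0.91 to 1.08).

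With a treatment main effect added and the clustering kept, null rejection was 33.5%, 47.5% and 46.3% in the three settings with day and period variance, and 5.2% with none. With period and treatment fixed, and subject, subject-by-period and clinic day random, the timepoint SE ratio was 0.97 to 1.05 in all four settings. Treatment rejection was then 3.7% to 6.0% in the same three settings.

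**The case against.** **The planned test errs on the safe side.** This stands. A reader might infer that the plan, as written, could falsely declare a LAT8881 effect. The documents do not support that: treatment is in neither the text nor the code of this model, so no such test is produced. The 24% to 39% figures also concern a 6-hour average, while the endpoints in SAP 7.2 (items 1 and 2) are changes at separate timepoints.

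**Anyone adding treatment would copy the primary model.** Protocol 13.5.1 points that way, and subject-by-period clustering gives a correct standard error for the 6-hour-average treatment contrast in balanced data. That stands too. It does not repair the timepoint contrasts: a subject-by-period cluster also holds two clinic days, so step 1 applies again. The clinic-day term is needed either way.

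**The size rests on an unknown.** Correct: with no day or period variance the coded standard errors are right, and the pre-dose covariate may absorb part of the day effect. Zero is still hard to assume. The sample-size inputs (SD 2, correlation 0.5) imply a within-subject variance between periods of 2²·(1−0.5) = 2, albeit for the weekly diary endpoint.

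**The model might be meant for each treatment or period separately.** Subject-by-week would then be the clinic day. But the code has no BY statement, and covariance between a subject's periods cannot be estimated from one period per subject.

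**It is a secondary analysis, to be read with caution under SAP 8.3.** True, and this limits how much the point matters.

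**Conclusion.** Wrong as written: a minor-to-moderate correction to a secondary analysis in 15 PK subjects. The conflict between text and code is plain on the page and needs no assumption. The numerical consequence for the planned tests is lost precision, about 13% to 45% on the standard errors of contrasts between timepoints, conditional on the assumed d/e of 0.5 to 2, balanced data and no separate period variance. It would be too broad to say that all the standard errors are wrong, since the week contrast and the 6 h mean are close to correct.

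The false-positive risk is conditional on a later edit that adds treatment and leaves the random line alone. It deserves a warning because secondary objective 1 is a comparison with placebo, which this model cannot make until treatment is added. That absence is the larger gap, and both repairs belong in one edit.

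**What to change.** Rewrite the block in SAP 11.6.1.2.1 and align the text with it:

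- CLASS: add `<study period>` and `<treatment>`.
- MODEL: add `<study period>`, `<week>*<timepoint>`, `<treatment>`, `<treatment>*<timepoint>`, `<treatment>*<week>` and `<treatment>*<week>*<timepoint>`.
- RANDOM: `random <subject> <subject>*<study period> <subject>*<study period>*<week>;`
- LSMEANS: request the LAT8881-placebo difference at each timepoint and visit.
- Text: name treatment and its interactions, and describe the three random terms.

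If the week contrast will be interpreted, consider keeping `<subject>*<week>` as a fourth random term. In the simulation, which included a subject-by-week SD of 0.3, leaving it out gave a week SE of 0.80 to 0.96 of its true value. The four-term version was not tested and may be hard to estimate in 15 subjects.

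The cost is one SAS block and a few sentences, changed before unblinding. No new data are needed.
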